Overview of study. The objective of this study is to expand the reach of SHE to address women's health disparities more broadly, and to create a sustainable model for dissemination of health promotion interventions for vulnerable populations. In the first aim (Year 1), we will run a pilot study to assess feasibility of the expanded content and electronic women's health literacy intervention delivered through text-Web modality with N~10 of our original SHE participants. Feasibility outcomes include uptake of intervention components, barriers and facilitators of implementation, problems with delivery, and necessary modifications. Pilot effectiveness outcomes will include an assessment of women's health literacy, operationalized as knowledge, beliefs, and self-efficacy for screening related to cervical, breast cancer, birth control, and STIs, post-intervention.

In the second aim (Year 2-3), we will conduct an RCT with N~200 newly recruited women to test the effectiveness of the SHE-Women electronic women's health literacy intervention: the intervention arm will get SHE-Women; the control arm will get a standard of care discharge planning session and health education booklet. Assessment of effectiveness will occur on two outcomes: a) Women's health literacy, operationalized as knowledge, beliefs, and self-efficacy for screening related to cervical, breast cancer, birth control, and STIs; and an increase in COVID-19 health literacy and increase in self-efficacy for prevention immediately post-intervention and 1-year post-intervention; b) Screening/ risk reduction for cervical, breast cancer, unintended pregnancy, and STIs at 1, 2, and 3-years post-intervention (follow-up complete by Year 5).

In the third aim (Year 3-5) we will track participants and conduct key stakeholder interviews to better understand the role and impact of human interaction in electronic interventions to answer the question: how much human "touch" is needed to make an intervention effective? Outcomes will include perception and uptake of intervention components, women's health literacy, screening, and risk reduction outcomes. Table 3 describes aims, activities, outcomes, and benchmarks.

Table 3. Aims, Activities, Outcomes, and Benchmarks

Activities	Outcomes	Benchmarks for success
Aim 1. Assess feasibility and pilot effectiveness of 'SHE-Women,' an electronic women's health literacy intervention.		

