
organizations (i.e. transitional living facilities, DV shelters, social support centers, etc.)
 
 • Randomize participants to intervention and control arms • Deliver SHE-Women to N~100 women via text-Web platform; deliver standard of care discharge planning session to N~100 women • Conduct baseline, post-intervention, 1, 2, 3 year assessments of women's health literacy and screening/risk reduction outcomes • Conduct N~30 stakeholder interviews to determine efficacy of COVID-19 module 	
 • Screening/risk reduction for cervical, breast cancer, unintended pregnancy, STIs and COVID-19 	
 • Manuscript #2 strategies for recruiting women leaving jails into health promotion interventions in Y3 • Conduct follow-ups for 3 years from intervention during Y1-Y5/ maintain 75-85% follow-up rate • Manuscript #3 effectiveness of SHE-Women at improving women's health literacy in Y3 • Manuscript #4 effectiveness of SHE-Women at improving women's health screening/risk reduction in Y4 • Placement of SHE-Women on NCI Research-Tested Intervention Programs site in Y5 • Manuscript #5 3-year outcomes of interventions in Y5
---	---	--

Aim 3. Understand the role and impact of human interaction in electronic interventions by tracking participants and interviewing key stakeholders.

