
 • Collect uptake data on use of text messages with health educator and attendance at community sessions • Track participant use of text-Web components • Conduct N~20 stakeholder interviews with participants to assess perceptions of human interaction in intervention delivery (5 intervention arm; 5 control arm; 10 utilizers of texting with health educator or community sessions) 	
 • Perception and uptake of intervention components, electronic or otherwise • Women's health literacy, screening/risk reduction outcomes. 	
 • Participant tracking and collection of intervention component uptake data to occur between Y2-Y5 • Key stakeholder interviews conducted between Y3Q4-Y4Q1 • Manuscript #6 perceptions of role of human interaction in intervention delivery in Y4 • Manuscript #7 uptake of text-Web components among high-risk women in Y5 • Manuscript #8 impact of human interaction (uptake of text messaging with health educator and/or attendance at community sessions) on women's health literacy and screening/risk reduction in Y5
--	--	--

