Power. The sample size for the Aim 1 feasibility study is based on our original SHE study pilot and expanded to allow for rigorous testing and refining of modality.²⁶ The sample size of N~200 for the Aim 2 RCT was determined to provide satisfactory power ($\geq 80\%$) for this study in addressing the specific aims, which depends on the following parameters: number of participants (n), number of measurements (t=3 for health literacy for screening; t=4 for screening/risk reduction practices), effect size (f) as group difference in change, correlation between repeated measures (r), and attrition rate. The effect sizes estimated from the original SHE study were in the small to moderate range—for health literacy (8 domains), average $f=0.13$ at immediately post-intervention and 0.16 at 1-year post-intervention; $f=0.17$ for cervix screening and 0.12 for condom use during the last intercourse at 1-year post-intervention. Although effect sizes for breast cancer screening and STI screening are not available from the original SHE study, we expect similar, small to moderate effect sizes for these outcomes. Thus, we conservatively assumed the smallest observed effect size of $f=0.12$ for our power calculation. The correlations between repeated measures observed in the original SHE study were $r=0.46$ on average, with the range of 0.39-0.75 between baseline and immediately post-intervention and 0.25-0.61 between baseline and 1-year post-intervention. Power analysis of these data ($f=0.13$, $t=3$ or 4, $r=0.46$) and G*Power 3.1.9.2 indicated that a sample of 124 women will produce $\geq 80\%$ power for both health literacy (80%) and screening/risk reduction behaviors (85%). In our original SHE study, the 3-year follow-up rate was 85%. Conservatively assuming a high attrition rate up to 40%, we will recruit ~200 women at baseline to adequately power the SHE-Women study—i.e., maintain $\geq 80\%$ power even with a low follow-up rate as small as 60%. As

Table 4. Expected attrition over study period

	Aim 1 feasibility Target N~20	Aim 2 RCT Target N~200	Aim 3 (same as Aim 2)
Consent and baseline	20	260	--
Intervention initiation	15	220	--
Post-intervention	10	200	--
1 year follow-up	--	170	--
2-year follow-up	--	160	--
3-year follow-up	--	150	--

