described above, missing data due to either attrition or nonresponse will be fully recovered via multiple imputation in our intent-to-treat analysis, which will provide additional power and remove any confounding effect of missing data on our statistical power. For Aim 3, the key stakeholder interviews will occur with enough research participants to reach thematic saturation. Based on prior experience with key stakeholder interviews, we believe N~20 interviews will accomplish this goal,²⁷ but have resources to interview additional participants. Additionally, our COVID-19 module interview suggests N~30 interviews will accomplish the goal of thematic saturation.

Outcomes and instruments. Aim 1 feasibility outcomes include uptake of intervention components, barriers and facilitators of implementation, problems with delivery, and necessary modifications.⁴⁵ Pilot effectiveness outcomes will include an assessment of women's health literacy, operationalized as knowledge, beliefs, and self-efficacy for screening related to cervical, breast cancer, birth control, and STIs, post-intervention.^{4,26} Aim 2 RCT outcomes include women's health literacy, immediately post-intervention and 1-year post-intervention; and screening/ risk reduction for cervical, breast cancer, unintended pregnancy, and STIs at 1, 2, and 3-years post-intervention. Aim 3 outcomes include perception and uptake of intervention components.⁴⁵

Feasibility and perception of intervention outcomes are defined below and assessed through participant tracking and key stakeholder interviews with a subset of participants.:

- *Uptake of integrated, multimedia electronic women's health literacy intervention:* documentation of number of participants who responded to text messages; clicks on Website; real-time assessment of knowledge; time elapsed between text messages and Website clicks; number of outreach messages (through text, phone, or Facebook); Facebook posts/messages; chats with health educator; total minutes of contact through text, Web, chat, Facebook with each participant; attendance at community sessions
- *Barriers and facilitators of implementation:* problems described by participants in setting up text message platform, Website, closed Facebook group; factors that make set up of text message platform, Website, closed Facebook group ease of use; ease of Website components use (content modules, assessments)

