Using quantitative data from the pilot trial of the SHE-Women text-Web intervention, we will conduct descriptive analysis and bivariate tests to explore women's health literacy (knowledge, beliefs, and self-efficacy) for screening related to cervical, breast cancer, birth control, and STIs (Aim 1). The results including effect sizes estimated for the outcome will be utilized for refinement of the intervention content and modality. To test the hypothesis that SHE-Women will be more effective than standard of care at improving outcomes (Aim 2), we will utilize mixed modeling techniques for repeated measures, separately for each outcome variable: health literacy for screening and screening/risk reduction practices. General/generalized models will evaluate the effects of the intervention by estimating overall group difference across measurements (i.e., group effect), change over time (i.e., time effect), and group difference in change (i.e., group-by-time interaction). In other words, we will evaluate whether the intervention vs. control group improves in outcomes over time. The models will account for the impacts of sociodemographic characteristics as well as other cross-cutting risk factors including tobacco use, alcohol use, criminal justice involvement, intimate partner violence, lack of continuous health care coverage or primary care contact, etc. (covariates), thereby providing unbiased estimates of the intervention effects. The models for screening/risk reduction behaviors will also consider knowledge about cervix cancer, breast cancer, birth control, or STI as an additional covariate for the respective outcome variable. Incorporating participant tracking data, descriptive analysis and bivariate tests will demonstrate the pattern and uptake of various intervention components as measured by number of participants who responded to text messages; clicks on the Website; interactive clicks on the Website, e.g. through real-time assessment of knowledge; time elapsed between text messages and Website clicks; number of outreach messages (through text, phone, or Facebook); Facebook posts/messages; chats with health educator; total minutes of contact through text, Web, chat, Facebook with each participant; and attendance at community sessions (Aim 3). General/generalized mixed modeling for repeated measures will assess the impacts of the uptake on each outcome variable of health literacy for screening and screening/risk reduction practices while controlling for the impact of sociodemographic characteristics and other risk factors. A proper covariance structure for repeated measures will be chosen for each outcome variable based on model fit (i.e., likelihood, Akaike Information Criterion, adjusted Bayesian Information Criterion). Statistical significance will be determined at 0.05 alpha level, and all analyses conducted using SAS 9.4⁵⁹

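### The Aim 2 screening/risk-reduction models adjust for domain knowledge without saying at which visit it is measured; a same-visit score would strip out the part of the intervention effect that runs through knowledge

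*Combined protocol and SAP*

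**What the plan says.** In the Data analysis section, the Aim 2 hypothesis is tested with mixed models for repeated measures, fitted separately to each outcome. They evaluate the intervention by "estimating overall group difference across measurements (i.e., group effect), change over time (i.e., time effect), and group difference in change". Sociodemographic and risk covariates follow, including health care coverage and primary care contact. The next sentence adds: "The models for screening/risk reduction behaviors will also consider knowledge about cervix cancer, breast cancer, birth control, or STI as an additional covariate". No time point is given for knowledge, coverage or primary care contact.

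Other sections show what kind of variable knowledge is:

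- Intervention arms and procedures: knowledge is the Day 1 content of the intervention arm.
- Overview of study: knowledge is the first component of women's health literacy, an Aim 2 outcome.
- Table 3, Aim 2 activities: "Conduct baseline, post-intervention, 1, 2, 3 year assessments of women's health literacy and screening/risk reduction outcomes".
- Outcomes and instruments: "Aim 2 RCT outcomes include women's health literacy, immediately post-intervention and 1-year post-intervention".
- Power: the effect size is defined as a group difference in change, with "t=3 for health literacy for screening; t=4 for screening/risk reduction practices".
- Progress report: in the original study, cervical cancer knowledge was among the best predictors of being up to date with Pap screening.
- Validation strategies: Pap knowledge was associated with accurate self-report of Pap screening, and 61% of self-reports matched the medical record.

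**The concern.** Taken together, these sections describe a path from intervention to knowledge to screening. Aim 2 asks whether SHE-Women improves screening and risk reduction as a whole, and that question includes this path. If the model conditions on knowledge measured after randomisation at the same visit as the outcome, the group and group-by-time terms estimate only what is left once knowledge is held fixed. Common causes of knowledge and screening can also bias that remainder. A working intervention could look weaker than it is, or miss significance.

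The plan leaves three versions of the covariate open, and they behave differently. If the choice is still open when outcome data are analysed, it can be made after the results are seen.

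**Working it through.** **1. The plan's own power figure.** Inputs from the Power section: N=124, r=0.46, t=3 or 4, alpha 0.05, two groups. The within-between interaction formula is lambda = f² × N × t / (1 − r), with df1 = t − 1 and df2 = (N − 2)(t − 1).

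- f=0.12, t=3: lambda = 0.0144 × 124 × 3 / 0.54 = 9.92; power 80.7% (stated: 80%).
- f=0.12, t=4: lambda = 13.23; power 87.3% (stated: 85%).
- f=0.13, also printed in that section: 86.9% and 92.4%, which does not match.

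So f≈0.12 reproduces the sample size. An f of 0.117 to 0.119 brings both powers within 2 points of the stated values. The effect being powered is the interaction.

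**2. Formula power if a same-visit score removes a share of the effect.** Replace f by f × (1 − share), with t=4 and r=0.46. The share is an assumption. N=150 is the year 3 figure in Table 4, and N=200 is the RCT target.

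| Share removed | f=0.12, N=124 | f=0.12, N=150 | f=0.12, N=200 |
|---|---|---|---|
| 0% | 87% | 93% | 98% |
| 10% | 79% | 87% | 95% |
| 25% | 61% | 71% | 84% |
| 50% | 30% | 36% | 46% |

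With f=0.13 and 25% removed, power falls from 96.5% to 78% at N=150 (lambda 18.78 to 10.56) and from 99% to 90% at N=200 (lambda 25.04 to 14.08).

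**3. The versions compared in one linear model.** Assumptions: screening at baseline and years 1 to 3, compound symmetry with r=0.46, unit SDs, and a knowledge-to-screening slope of 0.4. An interaction of f=0.12 equals a group difference of 0.12 / √(1/4 × 3/16) = 0.554 SD at each follow-up, or 0.554 × 3/4 = 0.416 SD averaged over the four visits. Knowledge gains of 0.1 to 0.64 SD were tried. The original study's literacy f of 0.13 to 0.16 corresponds to 0.26–0.32 SD if d = 2f, and to 0.52–0.64 SD if d = 4f. At a gain of 0.52 SD:

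- No knowledge covariate, or baseline score: interaction 0.554; average group term 0.416.
- Same-visit score: interaction 0.554 − 0.4 × 0.52 = 0.346; average group term 0.346 × 3/4 = 0.260.
- Fixed post-intervention score: interaction 0.554; average group term 0.416 − (0.4 × 0.46) × 0.52 = 0.320.

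Power for the 3-df interaction test at gains of 0.1 / 0.26 / 0.52 / 0.64 SD:

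- No covariate, baseline score or fixed post score: 93% at N=150 and 98% at N=200, at every gain.
- Same-visit score, N=150: 94 / 85 / 60 / 46%.
- Same-visit score, N=200: 98 / 94 / 74 / 59%.
- Year 1 score carried forward to years 2 and 3, N=150: 91 / 85 / 69 / 60%.

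The share mediated at these gains is 0.4 × gain / 0.554, that is 7 / 19 / 38 / 46%. At 0.1 SD the residual variance explained by knowledge offsets the small loss.

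**4. Does the fixed-post result carry over to yes/no outcomes?** A separate simulation used assumed parameters (20,000 women, four visits). In a random-intercept logistic model the interaction was 0.625 without knowledge, 0.623 with baseline knowledge, 0.625 with the fixed post score and 0.013 with the same-visit score. The fixed-post result therefore holds approximately there. In a marginal (GEE) model the interaction moved from 0.457 to 0.532 with the fixed post score, but baseline adjustment also moved it, to 0.550. That is non-collapsibility, not loss of a mediated effect. The plan specifies mixed models.

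**The case against.** The strongest reply is that the plan leaves a time point unstated and does not state an error. The wording is permissive, the sentence sits in a list of ordinary covariates, and the Progress report gives a prognostic reason to include knowledge. A baseline score fits all of that and does no harm. This stands: the documents do not commit to post-randomisation adjustment, and a reader who infers that they do goes too far.

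Three other stronger inferences also fail.

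- Not every post-randomisation score damages the powered effect. The fixed post-intervention version spares the interaction, exactly in a linear model with complete data and approximately in a random-intercept logistic model. The overall group term that it shifts averages in the baseline visit and is not what the trial is powered on.
- The phrase "thereby providing unbiased estimates of the intervention effects" comes before the knowledge sentence and attaches to the preceding covariates. It is not a claim about knowledge, though that list includes coverage and primary care contact, which are also undated and could be changed by the intervention.
- Not all of the knowledge-mediated difference need be real benefit. Because knowledge is tied to accurate self-report, some of it could be changed reporting.

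The size is open to challenge too. Both arms receive the booklet and are offered contact with a health educator, which narrows the knowledge contrast. Multiple imputation with intent-to-treat analysis aims at about 200 women, so N=150 is pessimistic and N=200 an upper bound. No section supports any particular mediated share, and carrying the year 1 score forward is not described anywhere.

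What remains is that a same-visit score is permitted. The repeated-measures model and the link between knowledge and reporting accuracy make it plausible, and it changes what is estimated.

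**Conclusion.** The point holds as an unresolved analysis choice that should be fixed. One permitted and plausible choice, the same-visit score, means the group and group-by-time terms no longer measure the total effect of the intervention. The baseline choice has no such consequence, and the fixed post-intervention choice affects mainly the overall group term.

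The size is illustrative only. It depends on the share of the effect mediated by knowledge, which the documents do not give. At 25% the formula loss is 22 points at N=150 (93% to 71%) and 14 points at N=200 (98% to 84%) with f=0.12, and somewhat less with f=0.13. At a knowledge contrast of 0.1 SD there is no material power loss. These figures assume t=4, r=0.46 and sphericity, and take no account of common causes of knowledge and screening.

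**What to change.** State in the Data analysis section that the primary Aim 2 screening/risk-reduction models use only the baseline knowledge score, and baseline values of other covariates the intervention could change, such as coverage and primary care contact. Report any model with follow-up knowledge only as a labelled mediation or sensitivity analysis. Settle this before outcome data are analysed.

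The cost is one sentence and one labelled secondary analysis. The baseline survey is already planned, so no new data are needed. The downside is that baseline adjustment does not address knowledge-related error in self-report. The sensitivity model explores that error but does not correct it.

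Two side points should be reconciled separately:

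- Table 3 lists literacy assessments through year 3, while the Overview, Power and Outcomes sections stop literacy at 1 year. The difference may only be between what is collected and what is defined as an outcome, but it decides whether same-visit knowledge exists at years 2 and 3.
- Validation strategies assigns the screening outcomes to Aim 1 when it describes knowledge weighting. The Overview and Outcomes sections place them under Aim 2, and the Overview also lists them for Aim 3 ("Outcomes will include perception and uptake of intervention components, women's health literacy, screening, and risk reduction outcomes").

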Participants who successfully initiate the intervention, over a 5-day period will be sent texts to their mobile phone or messaged through email or Facebook (participant preference) with a link to content on a SHE-Women Website. Content will correspond to Table 2, with tabs for Knowledge, Beliefs, Self-efficacy, Confidence navigating systems, and Wrap-up/review. Content will be delivered through a mix of short videos of the health educators and standardized patient actors discussing content (available in video and audio only format), interactive quizzes, and plain text. Although participants will be able to access content in all five areas, they will receive a daily text message for each area. For example, on Day 1, they will receive a text message to engage in Knowledge content; Day 2, a message to engage in Beliefs content; Day 3, a message to engage in

Self-Efficacy content; Day 4, a message to engage in Confidence navigating health systems content; and on Day 5, a message to complete Wrap-Up content and be invited to complete post-intervention assessments.

A second health educator will monitor whether participants access content after receiving the text messages. If participants have not accessed content within 24 hours of receiving a text message prompt, they will be sent a second text message invitation. If participants still haven't responded, they will receive a phone call from the lead health educator, or a video message through Facebook, that is directly geared toward the participant, re-inviting them to access content for that day.

The SHE-Women Website will also have a tab available to live-chat with a health educator 5 days a week for 8 hours a day. Participants will be able to send messages to the health educator through the SHE-Women Website, if they are not able to live chat. This feature will be available in addition to standard text-message access to a health educator during business hours. We will add weekend or evening hours if necessary.

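### The count of outreach messages is listed as an uptake measure, but reminders go out because content was not opened, so among women who start the intervention it tends to run against engagement

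*Combined protocol and SAP*

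**What the plan says.** Outcomes and instruments defines uptake of the electronic intervention by a list of nine items, and Data analysis repeats the list with small changes. Both include "number of outreach messages (through text, phone, or Facebook"). In Data analysis the list is introduced as the quantities that will "demonstrate the pattern and uptake of various intervention components as measured by". The next sentence makes uptake an exposure: "General/generalized mixed modeling for repeated measures will assess the impacts of the uptake on each outcome variable", "while controlling for the impact of sociodemographic characteristics and other risk factors". The plan does not say which of the nine items enter these models, in which direction each is scored, or whether outreach is handled apart from the rest.

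Intervention arms and procedures sets out when staff make contact. Women who initiate receive one scheduled prompt a day for five days, one per content area. After that: "If participants have not accessed content within 24 hours of receiving a text message prompt, they will be sent a second text message invitation". If there is still no response, the lead health educator telephones or sends a personal Facebook video. Intervention software platform gives automated reminders for unopened content as an example of what the system will do. Women who have not been in touch within three days of consent or release can also be contacted by staff.

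**The concern.** An uptake measure should record what a participant did with the intervention. Beyond any scheduled prompts, the outreach count largely records what staff did because the participant had not yet done anything. This is confounding by indication: the contact is given in response to low engagement, and low engagement is plausibly linked to poorer literacy and screening. The named adjustment covers sociodemographic characteristics and other risk factors. It does not cover earlier non-access, so it does not remove the problem.

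The stake is interpretive. Aim 3 asks how much human contact an electronic intervention needs, and the protocol lists the answer among its key findings. The personal call or video is the most human step in the reminder sequence, and it goes only to women who have not responded. If the outreach count enters an outcome model as uptake, a null or negative coefficient could be read as evidence that such contact does not help, when it may reflect only the rule that triggered it.

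Two neighbouring items share part of the difficulty. Total contact minutes do not distinguish who started the contact. The delay from prompt to site click is longer for less engaged women and has no value for a woman who never clicks.

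**Working it through.** The plan gives no figure for this point, so there is nothing to reproduce. The check follows the reminder rule through.

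**Inputs from Intervention arms and procedures:** 5 content areas; 1 scheduled prompt per area; 1 further text if the area is unopened at 24 hours; 1 call or video if it is still unopened.

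**Fixed patterns, same behaviour on all five days:**

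| Behaviour | Reminders | Messages including scheduled prompts | Areas opened |
|---|---|---|---|
| Opens at first prompt | 5 × 0 = 0 | 5 × 1 = 5 | 5 |
| Opens after second text | 5 × 1 = 5 | 5 × 2 = 10 | 5 |
| Opens after call or video | 5 × 2 = 10 | 5 × 3 = 15 | 5 |
| Never opens | 5 × 2 = 10 | 5 × 3 = 15 | 0 |

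The first and last rows show the opposing direction. The third and fourth rows show that it is not strict: two women with the same maximum count can differ by all five areas.

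**Expected values.** Let p be the probability of opening an area after any one contact, and q = 1 − p. The second text is sent with probability q and the call with probability q², so expected reminders are 5(q + q²). An area stays unopened with probability q³, so expected areas opened are 5(1 − q³). The documents do not give p; the values below are assumptions.

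| p | Expected reminders | Expected areas opened |
|---|---|---|
| 0.8 | 5(0.2 + 0.04) = 1.2 | 5(1 − 0.008) = 4.96 |
| 0.5 | 5(0.5 + 0.25) = 3.75 | 5(1 − 0.125) = 4.38 |
| 0.2 | 5(0.8 + 0.64) = 7.2 | 5(1 − 0.512) = 2.44 |

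Counting scheduled prompts adds 5 to every reminder figure and leaves the direction unchanged.

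**Simulation.** For 100,000 simulated women per scenario, p varied between women under an assumed Beta distribution, with openings independent given p. The Spearman correlation between reminder count and areas opened was:

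| Distribution of p | Correlation |
|---|---|
| Beta(1,1) | −0.87 |
| Beta(2,2) | −0.81 |
| Beta(5,5) | −0.72 |
| Beta(3,1) | −0.60 |

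The correlation is clearly negative in each scenario, but not −1.

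**The case against.** The strongest reply is that the plan defines no dose score. The nine items are listed separately, and nothing says they will be summed. Most of them, such as clicks, chats, posts and attendance, rise with engagement. The list is attached to descriptive and bivariate work, and Data analysis says earlier that Aim 3 uptake data will be summarised descriptively. Elsewhere the protocol keeps the ideas apart: Data collection speaks of recording uptake and outreach, and annoyance with outreach messages appears among delivery problems. All of this stands. It limits the point to one item, but it does not remove it, because the modelling sentence refers to uptake as just listed and excludes nothing.

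A reader might infer that the sign of the dose-response slope is reversed. The documents do not support that. A woman who opens each area only after the call reaches the same maximum as one who never opens anything, and the three-week access window allows late completion. The relation is a tendency, and the model coefficient cannot be derived from the protocol.

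A reader might also infer that the least engaged women in the trial have the highest counts. Women who never initiate are outside the daily sequence, and the number of contacts made to reach them is not stated. Nor is the term for outreach messages defined; it could include scheduled prompts or contacts about assessments.

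Finally, a reader might infer that the human-interaction paper is compromised. Table 3 gives the exposure for Manuscript #8 as texting with the educator and/or attendance at sessions, and outreach is not part of it. The contact-minutes item does not list telephone, so the educator's call is not named there either.

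On time to click, a longer delay meaning slower response is ordinary interpretation. The planned multiple imputation might be said to cover missing values, but for a woman who never clicked it could supply a click time that never occurred.

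**Conclusion.** The point holds for one of the nine listed uptake measures. Among women who initiate, the outreach count tends to run opposite to engagement: 0 reminders against 10 at the extremes (5 against 15 with scheduled prompts), and correlations with areas opened of −0.60 to −0.87 under the assumed opening probabilities. Used as an exposure without separation, its coefficient would be confounded by non-engagement. The bias is toward making staff contact look useless or harmful, on the assumption that engagement itself goes with better outcomes. The size of that bias cannot be computed from the documents.

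The consequence falls mainly on the Aim 3 uptake models and Manuscript #7, on uptake of the text-Web components. The randomised Aim 2 comparison is unaffected. The change is worth making before the Aim 3 models are run.

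**What to change.** In the uptake lists in Outcomes and instruments and in Data analysis:

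- Define outreach messages, saying whether scheduled prompts count. Take them out of the uptake set and report them as delivery effort.
- Use participant actions as the uptake exposures in the outcome models: content areas opened (0 to 5), minutes on the site, texts or chats started by the participant, and sessions attended. State which of these enter each model and in which direction.
- Split contact minutes into participant-initiated and staff-initiated. If both are modelled, enter them separately and do not interpret the staff-initiated coefficient as an effect.
- For women who never click, treat time to click as censored at the end of the three-week access window, rather than dropping them or imputing a time.

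The cost is a wording change to two lists and minor recoding. The platform is planned to track user interaction, and REDCap is planned to hold uptake and outreach records, so no new data collection should be needed provided the records show who initiated each contact.
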